3.9. Procedures

3.9.1 Timing of assessment

T0 baseline: VISIT enrollment; prior to start of treatment.

T1 week: first and second treatment sessions + physiotherapy

T2 weeks: third and fourth treatment sessions + physiotherapy

T3 weeks: VISIT fifth and sixth treatment session + physiotherapy

T6 weeks/FU: VISIT - end of physiotherapy

T8 weeks/FU: VISIT - end of clinical investigation.

3.9.2 Visiting Plan

T0 BASAL: Enrollment

During the daily clinical activity, the investigators participating in the study will select subjects with achilles tendinopathy through the criteria given in section 3.16 and identify those meeting the inclusion and exclusion criteria. After fully explaining the purposes, aims and procedures in the study investigation plan, the subject will be offered participation in the study. Finally, the selected subject will be asked to view the information form and date and sign the Informed Consent

The subject according to the randomization list will be assigned to Group A or Group B.

We will then proceed with the objective examination and collection of the information required by the appropriately prepared Electronic Data Collection Form.

It will be followed by:

- assessment of VISA-A score
- assessment of pain according to the VAS scale
- administration of the SF-12 quality of life test.

Previous or ongoing drug treatments of any kind will be documented.

In order to monitor the consumption of analgesic used during the clinical investigation in case of pain onset (paracetamol 1000 mg), a clinical diary will be given to the subject in which to indicate the day and dose of medication used.

The enrolled subject will be given a complex alphanumeric identification code consisting of the progressive enrollment number followed by an alphanumeric code generated through Random Sequence Generator at www.random.org.

All enrolled subjects will be trained to practice physiotherapy for the 6 weeks in the clinical study plan. Subjects belonging to Group A will be administered MD-Tissue.

T1 week:

This visit will consist of an evaluation regarding the tolerability of the administered product. During this week, the subject will have received the first two infiltrations stipulated in the clinical investigation plan. It will be verified that the clinical diary regarding analgesic consumption used has been properly completed and that the physiotherapy course is proceeding according to the clinical investigation plan.

T2 weeks:

This visit will consist of an evaluation regarding the tolerability of the administered product. During this week, the subject will have received the first two infiltrations stipulated in the clinical investigation plan. It will verify that the clinical diary regarding analgesic consumption used is correctly completed and that the physiotherapy course is proceeding according to the clinical investigation plan.

T3 weeks:

At this visit, the sixth injection treatment will be administered (the fifth was given during the week). The investigator will then proceed with the objective examination and assessment of the end points in the clinical investigation plan.

Including:

- assessment of the VISA-A score
- assessment of pain according to the VAS scale
- administration of the SF-12 quality of life test.

The consumption of analgesic medication used in case of pain onset will be assessed through clinical diary. The subject will be invited to continue the physiotherapy course for an additional 3 weeks.

T6 weeks/FU:

At this visit, the objective examination and assessment of the end points in the clinical investigation plan will be conducted.

Including:

- assessment of the VISA-A score
- assessment of pain according to the VAS scale
- administration of the SF-12 quality of life test.

The consumption of analgesic medication used in case of pain onset will be assessed through clinical diary.

T8 weeks/FU:

The investigator after 2 weeks will re-evaluate the subjects clinically. It will be evaluated, VISA-A score, pain VAS and SF-12 quality of life test will be administered.

In addition, the consumption of analgesic drug used in case of pain onset will be assessed through clinical diary.

The occurrence of Adverse Events will be assessed at each visit. All Adverse Events (AEs), Serious Adverse Events (SAEs), and Suspected Serious and Unexpected Adverse Reactions (SUSARs) that appeared between the date the Informed Consent was signed and the end of the clinical investigation will be recorded and reported.

The collected data should be entered by the Principal Investigator of each Experimental Center in the Electronic Data Collection Form provided by Guna S.p.a.

Specifically, it is planned to obtain a data collection that is schematically described in the following table (Tab. 1), which shows the records to be made at each visit:

EXPERIMENTAL PROCEDURES	VISIT			VISIT	VISIT	VISIT
	T 0	T 1 WEEK	T 2 WEEKS	T 3 WEEKS	T6/FU WEEKS	T8/FU WEEKS
	Enrollment	1°-2° infiltration	3°-4° infiltration	5°-6° infiltration	Physiotherapy termination	End of clinical Investigation.
Clinical and ultrasonographic diagnosis of Achilles tendon pathology	X					
Evaluation of Inclusion criteria	X					
Signing of informed consent	X					

Signature of Consent to the processing of personal data	X					
Collection of socio-demographic data	X					
Medical history collection	X					
Evaluation VISA-A score	X			X	X	X
Evaluation VAS	X			X	X	X
SF12 questionnaire administration	X			X	X	X
Infiltrative treatment		X	X	X		
Physiotherapy		X	X	X	X	
Clinical diary evaluation	X	X	X	X	X	X
Evaluation of concomitant pathologies		X	X	X	X	X
Adverse Event Evaluation (AE/SAE)		X	X	X	X	X

Tab.1 Data collection during the Study

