3.3. Design of the clinical investigation

The multicenter, randomized clinical investigation is prospective, and will have a total duration of 8 weeks.

After enrollment, subjects will be randomized and assigned to two experimental groups:

- **Group A** which, alongside physiotherapy (eccentric strengthening protocol) will receive MD-Tissue Collagen Medical Device.
- **Group B** which, will implement only physiotherapy (eccentric strengthening protocol).

Variables will be assessed at baseline (T0 time), after 1 week (T1w), after 2 weeks (T2w), after 3 weeks (T3w), or at the end of injection treatment, and after 6 weeks after enrollment (T6w/FU). Further evaluation will be carried out after 2 weeks, or after 8 weeks (T8w/FU) from the start of the clinical investigation.

After enrollment, subjects in both groups will begin a 6-week physiotherapy course (eccentric strengthening protocol). Each session will consist of Achilles tendon stretching exercises. See § 3.12.

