3.6. Inclusion Criteria

- Male and female subjects aged 18 to 70 years.
- Subjects with tendon pain for not more than 24 weeks;
- Subjects with clinically diagnosed and ultrasonographically confirmed. insertional/noninsertional/mystic tendinopathy;
- Subjects with a VISA A score between 50 and 75;
- VAS \geq 5;
- Subjects able to understand and answer the SF12 questionnaire.
- Subjects able to understand and sign the informed consent.

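### Section 3.9.2 places assignment to Group A or B before the T0 questionnaires: SF-12, and VISA-A and VAS if scored afresh, can be answered with the arm known

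*Protocol*

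**What the plan says.** The T0 paragraph of section 3.9.2 reads the same in the Protocol and in the Combined protocol and SAP. Eligible subjects are identified, the study is explained and consent is signed. Then: "The subject according to the randomization list will be assigned to Group A or Group B". The next sentence is "We will then proceed with the objective examination and collection of the information required by the appropriately prepared Electronic Data Collection Form". VISA-A, VAS and SF-12 are listed as following that step. The paragraph ends with "Subjects belonging to Group A will be administered MD-Tissue".

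Three other places bear on the order:

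- Section 3.3: "After enrollment, subjects will be randomized and assigned to two experimental groups". T0 is the enrollment visit, so this can be read as baseline scores first and randomization second.
- Section 3.9.1: "T0 baseline: VISIT enrollment; prior to start of treatment". This puts T0 before treatment but does not say before assignment.
- Table 1: one T0 column holds "Evaluation of Inclusion criteria" and a single mark each for VISA-A, VAS and SF-12. It has no randomization row and gives no order within the visit.

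The inclusion criteria in section 3.6 contain "Subjects with a VISA A score between 50 and 75" and a VAS of at least 5. SF-12 appears there only as an ability to understand and answer it, with no score limit.

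**The concern.** Baseline adjustment relies on the baseline being unaffected by treatment assignment. Here all three T0 measures are reported by the subject, Group B receives physiotherapy alone, and neither masking nor a sham injection is described. A subject told the assignment therefore knows the arm. If the questionnaires come next, as 3.9.2 lists them, hope or disappointment about the allocation can shift the reported scores differently in the two groups.

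T0 is the reference for the primary endpoint (VISA-A at T8, section 3.14.1) and for the VISA-A, VAS and SF-12 secondary endpoints. A shift at T0 that depends on the arm would carry over into the treatment comparison. Two sites could also both comply with the plan while collecting baseline under different conditions, one following 3.9.2 and the other 3.3.

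**Working it through.** **Order in the text.** Section 3.9.2 links its steps with words of sequence: consent, assignment, then examination and data collection, followed by the questionnaires. No visible text requires the T0 scores to precede assignment. Section 3.3 permits that order without stating it, 3.9.1 concerns treatment rather than assignment, and Table 1 is silent.

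**Which measures are exposed.**

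- SF-12: no score is needed for eligibility, so the only T0 value is the one listed after assignment. It is exposed under the 3.9.2 order.
- VISA-A and VAS: the limits of 50 to 75 and at least 5 are applied before assignment, so some value exists by then. If it is carried over as T0, there is no exposure. If the scores are taken again, as the later list allows, there is. Neither document says which.

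**Plan's own figure.** Inputs from section 4.14: 28 per arm, difference 12, SD 15, R² 0.2, alpha 0.05.

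- Residual SD = 15 × √(1 − 0.2) = 13.42
- SE of the difference = 13.42 × √(2/28) = 3.586
- Non-centrality = (12 / 3.586)² = 11.2, with 1 and 53 df
- Power = 90.75%, as stated in the plan

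**Illustration for VISA-A.** The following are assumptions and not in the documents: T0 VISA-A is the covariate (section 4.15 names none), T0 is scored afresh, one arm's mean reported T0 moves by *d* points, and T8 reporting is not shifted.

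- Slope = √0.2 × 15 / baseline SD
- Size of the ANCOVA bias = slope × *d*
- Baseline SD 7.2 (uniform on 50 to 75: 25/√12) gives slope 0.930. Baseline SD 12.5 (half the subjects at 50 and half at 75) gives slope 0.537.

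| *d* | Bias, SD 12.5 | Bias, SD 7.2 | Type I error, SD 12.5 | Type I error, SD 7.2 | Power at a true 12 if bias is against the device (SD 12.5 / SD 7.2) |
|---|---|---|---|---|---|
| 1 | 0.54 | 0.93 | 5.2% | 5.7% | 88% / 86% |
| 2 | 1.07 | 1.86 | 6.0% | 8.0% | 85% / 79% |
| 3 | 1.61 | 2.79 | 7.3% | 11.9% | 81% / 71% |
| 5 | 2.68 | 4.65 | 11.4% | 24.7% | 72% / 52% |

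Type I error is two-sided, from the non-central F with SE 3.586.

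**These are not bounds.** A baseline SD below 7.2 is possible in a 25-point window. At SD 5 the slope is √0.2 × 15 / 5 = 1.34, and a 5-point shift gives a bias of 6.7 points and a type I error of about 45%.

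**Same shift at T0 and T8.** The change-score bias is then *d* − *d* = 0, and the ANCOVA bias is *d* × (1 − slope). Per point of shift this is 0.46 at SD 12.5, 0.07 at SD 7.2 and −0.34 at SD 5, so even the sign depends on the SD. Simulated type I error at SD 12.5 and 7.2 is 6.6% and 5.0% for 3 points, and 9.3% and 5.1% for 5 points.

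**The case against.** The strongest reply is that the primary endpoint is already protected. Eligibility is settled before assignment, it needs a VISA-A and a VAS score, and Table 1 lists one T0 entry for each. The simplest reading is that the eligibility score is the T0 score and is merely entered on the form later. This largely stands for those two measures: it makes carry-over plausible, but no text states it, and 3.9.2 lists both assessments after assignment. It does not help SF-12.

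Second, the T0 paragraph may not be chronological. Its last line mentions MD-Tissue for Group A, whereas Table 1 starts infiltration at T1. The text is also a loose translation, and nothing says when the subject learns the arm. That lowers confidence that sites would follow this order, but it is also a reason to state the order. Figure 1 and Annexes A and I are not visible in the text reviewed and might settle it.

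Third, every follow-up score is self-reported without masking, so a clean baseline removes only part of the reporting bias. That is true, but follow-up cannot be masked by a change of wording, whereas the baseline report can be protected that way.

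A reader might go further and infer that the primary baseline is necessarily collected unblinded, that the primary result will be biased, or that the trial is underpowered. The documents support none of these. A fresh VISA-A after assignment is only possible, no shift is documented, and the power calculation reproduces.

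**Conclusion.** The point holds as a weakness of wording that can be removed at very little cost. Under the order in 3.9.2, SF-12 is clearly open to being answered with the arm known. VISA-A and VAS are open to it only if their T0 values are taken afresh.

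The size and direction of any bias are unknown. The tabulated figures rest on assumed shifts, an assumed covariate and assumed baseline SDs. They show that the effect could range from negligible to material, and they bound nothing. The planned power of 90.75% and the sample size are unaffected. Confidence is medium, because the order rests on the sequence words of one paragraph and on attachments that could not be seen.

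**What to change.** In 3.9.2 of both documents, move the assignment sentence after the questionnaires and add wording such as: *VISA-A, VAS and SF-12 are completed and saved in the e-CRF before the assignment to Group A or B is disclosed to the subject; the VISA-A and VAS used for eligibility are the recorded T0 values.* Align 3.3 and 3.9.1 with this, add a randomization row to Table 1 after the T0 questionnaires, and check that Figure 1 and Annexes A and I show the same order.

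The cost is small: same visit, same questionnaires, with three forms saved before the assignment is opened. If scoring follows consent, a few consented subjects may not be randomized. The documents give no rate; if 5% to 20% failed the score limits (assumed), 72 randomized would need 72/0.95 = 75.8, so 76, to 72/0.80 = 90 consents.

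The change protects only the subject's own baseline report. Follow-up stays unblinded, and the randomization list held by each Principal Investigator (section 3.8) is a separate problem that it does not cure.

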3.11. Gruppi in studio

- **Group A (Collagen Medical Device):**

This Experimental Group will be treated with subcutaneous (s.c.) injections of 2 ml volume of:

- MD-Tissue (GUNA, Milan-Italy)

[figure not shown]
Composition for 2 ml: collagen 100 micrograms

Excipients: Ascorbic acid, Magnesium gluconate, Pyridoxine hydrochloride, Riboflavin, Thiamine hydrochloride, NaCl, Water for injection.

Subjects will be treated with No. 6 peri-tendon injections (2 infiltrations per week for three weeks).

- **Group B:**

This Experimental Group will implement only physiotherapy (eccentric strengthening protocol) for a period of 6 weeks.

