3.14.1. Secondaries End Points

- Evaluation of VISA-A score at time T3w and T6w/FU compared to time T0
- Assessment of the VAS score at time T3w, T6w/FU and T8w/FU compared to time T0
- Evaluation of the SF12 questionnaire at time T3w, T6w/FU, and T8w/FU compared to time T0.
- Evaluation of the fraction of subjects in each group achieving Minimal Clinical Disease (MCD) considering that the MCD of the VISA-A questionnaire is 18.5 (90% MCD).
- Assessment of analgesic drug unit consumption based on clinical diary at time T3w, T6w/FU and time T8w/FU (paracetamol 1000 mg. will be used as "rescue dose" in case of onset/recurrence of pain).
- Evaluation of the fraction of subjects in each group who drop out early in relation to Adverse Events (AE/SAE/SUSAR).

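### At T3 the plan places the sixth injection before the endpoint assessment, so any acute injection response enters the T3 secondary comparisons in Group A only; scoring first removes it

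*Protocol*

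**What the plan says.** Under T3 weeks, section 3.9.2 of both documents opens: "At this visit, the sixth injection treatment will be administered (the fifth was given during the week"). The next sentence is "The investigator will then proceed with the objective examination and assessment of the end points in the clinical investigation plan", followed by a list of VISA-A, VAS and SF-12.

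The arms differ in what precedes that assessment. For Group A, section 3.11 says: "This Experimental Group will be treated with subcutaneous (s.c.) injections of 2 ml volume of" MD-Tissue, and "Subjects will be treated with No. 6 peri-tendon injections (2 infiltrations per week for three weeks"). For Group B: "This Experimental Group will implement only physiotherapy (eccentric strengthening protocol) for a period of 6 weeks". No sham procedure is described.

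All three scales have T3 as a secondary time point in section 3.14. For VISA-A the entry is "Evaluation of VISA-A score at time T3w and T6w/FU compared to time T0"; for pain it is "Assessment of the VAS score at time T3w, T6w/FU and T8w/FU compared to time T0"; and for quality of life it is "Evaluation of the SF12 questionnaire at time T3w, T6w/FU, and T8w/FU compared to time T0". Section 4.15 analyses VISA-A and VAS by repeated-measures ANOVA between and within groups, and SF-12 by repeated-measures ANOVA or Friedman's test. The primary endpoint is VISA-A at T8 compared with T0.

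Section 3.9.1 and Table 1 place the injection and the scores at T3 without ordering them. Section 3.3 describes T3 as the end of injection treatment.

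**The concern.** A Group A subject who is handled as the text directs rates pain and function after a peri-tendon injection given at the same visit, into a region that section 3.13 expects to be tender. A Group B subject completes the same scales with no procedure beforehand. Baseline is taken before treatment in both arms, so subtracting T0 does not remove the difference. Randomization does not remove it either, because it arises after allocation.

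At stake is what the T3 contrast means. It is the only scored visit within the injection course. As written, it cannot separate the effect of the course from the immediate response to its last needle. That response could be soreness, which works against the device, or relief and expectation, which work for it. With the sign unknown, no later analysis can correct for it.

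**Working it through.** **1. Does the text fix an order, and does anything reverse it?**
- Section 3.9.2, T3: injection, then examination and endpoints. An order is given, but no interval.
- Section 3.9.1 and Table 1: both items at T3, no order.
- No section asks for scoring before the injection, a waiting time, or a VAS recall period that excludes the injection.

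The order therefore stands as written.

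**2. Which comparisons are exposed?** Table 1 shows injections at T1, T2 and T3, and scores at T0, T3, T6 and T8. T3 is the only scored visit that has an injection. The T8 primary endpoint falls 8 − 3 = 5 weeks after the T3 visit.

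**3. The plan's own figure (section 4.14).** Inputs: 28 per arm, difference 12, SD 15, R² 0.2, alpha 0.05.
- Residual SD = 15 × √(1 − 0.2) = 13.416.
- Noncentrality = 28 × 12² / (2 × 13.416²) = 11.2.
- Noncentral F with 1 and 2 × 28 − 3 = 53 degrees of freedom: power 0.9075, as stated.
- Dropout: 28 / 0.8 = 35, against 36 planned.

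None of these inputs involves T3, so the sample size does not depend on the order of procedures.

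**4. Illustration for the T3 VAS.** The documents give neither an acute injection effect nor a VAS SD. Assumed: a uniform shift b of 0.5 or 1.0 points in Group A at T3, SD 2.0 to 2.5, 28 per arm and no true effect. SE = SD × √(2/28); rejection probability = Φ(b/SE − 1.96) + Φ(−b/SE − 1.96).

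| Assumed SD | SE | b = 0.5 | b = 1.0 |
|---|---|---|---|
| 2.0 | 0.535 | 15% | 46% |
| 2.5 | 0.668 | 12% | 32% |

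The nominal rate is 5%. As b approaches zero, the rejection rate returns to 5%.

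**5. The planned analysis is not a stand-alone T3 test.** Take the group effect averaged over T3, T6 and T8:
- A 1.0-point shift at T3 alone moves the average by 1.0/3 = 0.33 points.
- SE of the average = SD × √(2/28) × √((1 + 2ρ)/3), where ρ is the correlation between visits, assumed 0.3 to 0.7.
- Smallest SE (SD 2.0, ρ 0.3): 0.390, rejection 14%. Largest SE (SD 2.5, ρ 0.7): 0.598, rejection 9%.

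The group-by-time interaction is not diluted in this way. Under equal correlation between visits and the same ranges, a 1.0-point shift leads to rejection in about 22–69% of trials. How far the T3 shift matters therefore depends on which term of the ANOVA is read.

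**The case against.** The strongest case is that this is a small matter of wording. The text is a rough translation, and the T0 narrative in 3.9.2 uses the same loose connective, so one *then* should not be read as a timed procedure. That stands as far as timing goes. A reader might infer that Group A is scored straight after the needle, or within minutes, but the documents give an order and no interval. It does not remove the order itself, which nothing else in the plan contradicts.

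A reader might also infer that the trial's main result is biased. The documents do not support this, because the primary endpoint is at T8 and neither T6 nor T8 has an injection.

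Nor do they support saying that all three scales are affected equally. The VISA-A, VAS and SF-12 forms are annexes that are not shown, so whether a same-visit injection moves VISA-A or SF-12 depends on item wording and recall windows that cannot be checked here.

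The size is assumed throughout. Soreness in some subjects and relief in others could partly cancel, and a shift near zero is not excluded. This stands, and the rejection rates are illustrations only.

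Finally, measuring after the full course may be deliberate, since section 3.3 calls T3 the end of injection treatment. Scoring first would also leave open-label expectation from five earlier injections and any soreness remaining from the fifth, given that same week. Both points stand. The change removes only the last injection's contribution, and section 3.3 has to be brought into line with it.

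**Conclusion.** The point holds for the T3 secondary comparisons and for the repeated-measures tests that include T3. Followed as written, the plan lets any acute response to the sixth injection into one arm of the T3 contrast. This is most direct for VAS and possible for VISA-A and SF-12. The T6 visit, the T8 primary endpoint, the 90.75% power and the 36 per arm are untouched.

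The documents give no size or direction. On the assumptions set out above, a stand-alone T3 VAS test with no true effect would reject in about 12–46% of trials. A group effect averaged over T3, T6 and T8 would reject in about 9–14% at the larger shift of 1.0 point. These figures show only that a modest shift could matter; they do not predict one.

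The change is worth making because it costs almost nothing and removes an avoidable difference between the arms.

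**What to change.** In section 3.9.2, T3 weeks, of both documents, state that VISA-A, VAS, SF-12 and the objective examination are completed in both arms before any injection due at that visit. Repeat this in a footnote to Table 1. The number and timing of injections do not change.

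Reconcile section 3.3 of both documents, which presents T3 as the end of injection treatment: the T3 score would then reflect five completed injections, with the sixth following at the same visit.

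The cost is one sentence, one footnote and a wording change in 3.3, with no extra visit, staff or patients. The small downside is that T3 no longer measures the state after all six injections; T6 and T8 still do.
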